## List of Abbreviations

anti-TNF	anti-Tumor-Necrosis Factor
aPTT	Activated Partial Thromboplastin Time
AE	Adverse Event
AESI	Adverse Event of Special Interest
ADR	Adverse Drug Reaction
ALT	Alanine Aminotransferase
ANC	Absolute Neutrophil Count
ASCO	American Society of Clinical Oncology
AST	Aspartate Aminotransferase
BCG	Bacillus Calmette-Guérin
BN	Bavarian Nordic
BUN	Blood Urea Nitrogen
CEA	Carcinoembryonic Antigen
CI	Confidence Interval
CNS	Central Nervous System
COPD	Chronic Obstructive Pulmonary Disease
CR	Complete Response
CRA	Clinical Research Associate
CRO	Contract Research Organization
CT	Computed Tomography
CTCAE	Common Terminology Criteria for Adverse Events
CTLA-4	Cytotoxic T lymphocyte-associated Protein 4
DDMVAC	Dose-dense Methotrexate, Vinblastine, Doxorubicin and Cisplatin
dL	Deciliter
DILI	DrugInduced Liver Injury
DLT	Dose Limiting Toxicity
DNA	Deoxyribonucleic acid
ECG	Electrocardiogram
ECOG	Eastern Cooperative Oncology Group
eCRF	Electronic Case Report Form

EDC	Electronic Data Capture
EE	Efficacy Evaluable Set
EMA	European Medicines Agency
EMR	Electronic Medical Record
EOT	End of Treatment
EU	European Union
FAS	Full Analysis Set
FDA	Food and Drug Administration
FFPE	Formalin-fixed Paraffin-embedded
FPV	Fowlpox Virus
FU	Follow-Up
GC	Gemcitabine plus Cisplatin
GCP	Good Clinical Practice
g	Grams
HBcAb	Hepatitis B Core Antibody
HBsAg	Hepatitis B Surface Antigen
HBV	Hepatitis B Virus
HCV	Hepatitis C Virus
HIPAA	Health Insurance Portability and Accountability Act
HIV	Human Immunodeficiency Virus
IB	Investigator Brochure
ICAM-1	Intercellular Adhesion Molecule-1
ICF	Informed Consent Form
ICH	International Conference of Harmonization
IMAEs	Immune-Mediated Adverse Events
IFN	Interferon
IL	Interleukin
IMP	Investigational Medicinal Product
Inf.U	Infectious Units
IND	Investigational New Drug
INR	International Normalized Ratio
IRB	Institutional Review Board
IUD	Intrauterine Device

IV	Intravenous
L	Liter
LA	Locally Advanced
LLN	Lower Limit of Normal
LDH	Lactate Dehydrogenase
LFA-3	Leukocyte Function-Associated Antigen 3
LTFU	Long Term Follow-up
M	Metastatic
MCH	Mean Corpuscular Hemoglobin
MCV	Mean Corpuscular Volume
MedDRA	Medical Dictionary for Regulatory Affairs
mg	Milligram
mL	Milliliter
mmol	Millimole
MMR	Mismatch repair
MP	Medical Product
MRI	Magnetic Resonance Imaging
MSI	Microsatellite instability
MUC-1	Mucin-1
MVA	Modified Vaccinia Ankara
MVAC	Methotrexate, Vinblastine, Doxorubicin, plus Cisplatin
NCCN	National Comprehensive Cancer Network
NCI	National Cancer Institute
NCI CTCAE	NCI Common Terminology Criteria for Adverse Events
NYHA	New York Heart Association
OS	Overall Survival
OR	Objective Response
ORR	Objective Response Rate
PBMC	Peripheral Blood Mononuclear Cell
PCR	Polymerase Chain Reaction
PD	Progressive Disease
PD-1	Programmed Death 1
PD-L1	Programmed Death Ligand 1

PE	Physical Examination
PFS	Progression-Free Survival
PHI	Protected Health Information
PI	Principal Investigator
PR	Partial Response
PSA	Prostate Specific Antigen
PT	Prothrombin Time
PV	Pharmacovigilance
RBC	Red Blood Cells
RDW	Red Blood Cell Distribution Width
RECIST	Response Evaluation Criteria In Solid Tumors
RNA	Ribonucleic Acid
SAE	Serious Adverse Event
SADR	Serious Adverse Drug Reaction
SUSAR	Suspected Unexpected Serious Adverse Reaction
SC	Subcutaneous
SGOT	Serum glutamic oxaloacetic transaminase
SGPT	Serum glutamic-pyruvic transaminase
SMT	Safety Monitoring Team
SOP	Standard Operating Procedure
T3	Triiodothyronine
T4	Thyroxine
TAA	Tumor-Associated Antigen
TCID 50	Tissue Culture Infectious Dose
TCR	T cell Receptor
TEAE	Treatment Emergent Adverse Event
TIL	Tumor-Infiltrating-Lymphocytes
TNF	Tumor Necrosis Factor
Trial Vaccine	MVA-BN-CV301 and FPV-CV301
Trial Medication	Atezolizumab
Trial Product	MVA-BN-CV301, FPV-CV301, and Atezolizumab
TRICOM™	Triad of Costimulatory Molecules
TSH	Thyroid –Stimulating Hormone

TURBT	Transurethral Resection of Bladder Tumor
μL	Microliter
μm	Micrometer
UC	Urothelial Cancer
ULN	Upper Limit of Normal
US	United States
USA	United States of America
USPI	United States Prescribing Information
UTI	Urinary Tract Infection
WBC	White Blood Cell
WOCBP	Women of child-bearing potential

---

## 1.4 Protocol Synopsis

Title	A Phase 2, Multicenter, Single-Arm Trial of CV301 in Combination with PD-1/L1 Blockade in Patients with Locally Advanced or Metastatic Urothelial Bladder Cancer
Clinical phase	Phase 2
Sponsor	Bavarian Nordic A/S 
Number of sites	Approximately 12
Vaccination dose, schedule and administration route	
Prime with MVA-BN-CV301 (nominal titer <math>1.6 \times 10^9</math> Inf.U) given subcutaneously (SC) on Day 1 and Day 22. One dose = four 0.5 mL injections. One injection = nominal titer <math>4 \times 10^8</math> Inf.U in 0.5 mL.
 
Boost with FPV-CV301 (nominal titer of <math>1 \times 10^9</math> Inf.U in 0.5 mL, given SC every 21 days for 4 doses (on days 43, 64, 85, and 106), followed by boosts every 6 weeks until 6 months on trial (i.e., days 148 and 190), then every 12 weeks until completion of 2 years. One dose = one 0.5 mL injection.
 
Atezolizumab fixed dose of 1200 mg intravenous on Day 1 of each 21-day cycle. No dose reduction permitted.

Trial duration	Approximately 104 weeks before starting the long term follow up.
Trial Population	
Patients with Locally Advanced or Metastatic Urothelial Cancer (UC) including bladder, ureter, renal pelvis and urethra.
 
Cohort 1: Ineligible for cisplatin-containing chemotherapy (first-line treatment)
 
Cohort 2: Previously treated with standard first-line cisplatin-based chemotherapy, PD-1/L1 Naïve (second-line treatment)

Number of Subjects:	Approximately up to 68
Primary objectives	Objective Response Rate (ORR; Complete Response [CR] + Partial Response [PR] Rate) as per Response Evaluation Criteria in Solid Tumors version 1.1 (RECIST 1.1)

Secondary objectives	Progression-Free Survival (PFS)  Overall Survival (OS)  Duration of Response  Safety of the treatment combination of CV301 with atezolizumab
Exploratory objectives	Analysis of biopsy tissue for differences between pre- and post-treatment samples correlation to patient survival e.g.: 

• T cell receptor (TCR) clonality

• Tumor-Infiltrating-Lymphocytes (TILs)

• Protein expression for e.g. Programmed Death Ligand 1 (PD-L1) and other biomarkers

• Gene expression profiling for molecular subtyping

 Analysis of tumor DNA for Tumor mutational burden; DNA damage response gene mutations, MSI status, MMR deficiency status  Analysis of peripheral blood mononuclear cells (PBMCs) / serum for differences between pre- and post-treatment samples correlation to patient survival e.g.: 

• Antigen-specific immune responses to carcinoembryonic antigen (CEA) and mucin-1 (MUC-1) as well as to other tumor-associated antigens (TAAs) to assess antigen cascade

• Immunophenotyping of immune cell subsets by flow cytometry

• Soluble biomarkers (e.g. cytokines and classical tumor markers)

• TCR clonality

• PD-1/L1 staining

Primary endpoint	Proportion of subjects with a confirmed OR (CR+PR) as per investigator assessment according to RECIST 1.1.

---

Secondary endpoints	
Safety of the combined treatment as measured by:
 

• Adverse Events (incidence, severity, and seriousness of treatment emergent adverse events [TEAEs])

• Laboratory Measures (summaries and shifts from baseline)

• Vital Signs (summaries)

 
OS defined as the time from start of treatment to the time of death from any cause.
 
Duration of response defined as the time from the initial occurrence of documented complete response (CR) or partial response (PR) (whichever occurred first) until documented disease progression or death due to any cause on trial, whichever occurred first.
 
PFS defined as the time from start of treatment to the first event of death or progressive disease (PD) per RECIST 1.1.
 
Percentage of participants with OS and PFS at 6 (PFS only), 9 (PFS only), 12, 18 and 24 months.
 
Immune-related Response Criteria assessment of response rate per iRECIST, delayed responses (pseudo-progressions), duration of response and PFS.

Trial design	Phase 2, Multicenter, Single-Arm, 2 Cohorts, Two-stage
Inclusion criteria – ALL subjects	

1. The subject has read, signed and dated the Informed Consent Form (ICF), having been advised of the risks and benefits of the trial in a language understood by the subject. The ICF must be signed prior to any protocol specific assessments.

2. Age <math>\geq</math> 18 years at date of ICF signature having the ability to comply with protocol.

3. Histologically or cytologically documented locally advanced (T4b, any N M0; or any T, N 1–3 M0) or metastatic (M1, Stage IV; or metastatic recurrence after locoregional treatment) UC (including renal pelvis, ureters, urinary bladder, urethra). 
Note about the change in the definition of Locally Advanced from TNM v7 to the current v8, while all those cases were Stage IV in v7, with TNM v8 they are reclassified as Stage IIIA (T1-4a N1 M0) and Stage IIIB (T1-4a N2-3 M0).

a. Patients with mixed histologies were required to have a dominant transitional cell pattern.

- b. Locally advanced bladder cancer that was inoperable on the basis of involvement of the pelvic sidewall or adjacent viscera (clinical stage T4b) or bulky nodal metastasis (N2–N3).
4. Life expectancy  $\geq$  12 weeks.
5. Measurable disease, as defined by RECIST 1.1. Previously irradiated lesions cannot be counted as target lesions unless there has been demonstrated progression in the lesion since radiotherapy and no other lesions are available for selection as target lesions.
6. Demonstrate adequate organ function as defined in [Table 1](#). All screening labs should be performed within 14 days prior to the first trial product:

**Table 1: Adequate Organ Function Laboratory Values**

System	Laboratory Value
Hematological	
Absolute neutrophil count (ANC)	$\geq$ 1,500 cells/ $\mu$ L
Platelets	$\geq$ 100,000/ $\mu$ L
Hemoglobin	$\geq$ 9.0 g/dL
WBC	$>$ 2,500/ $\mu$ L
Lymphocyte count	$\geq$ 300/ $\mu$ L
Hepatic	
Total bilirubin	$\leq$ 1.5 x Upper Limit of Normal (ULN) OR Patients with known Gilbert disease who had serum bilirubin level $\leq$ 3 x ULN
Aspartate aminotransferase (AST)/ Serum glutamic oxaloacetic transaminase (SGOT) and Alanine aminotransferase (ALT)/Serum glutamic-pyruvic transaminase (SGPT)	$\leq$ 2.5 x ULN with the following exceptions: $\leq$ 5 x ULN for subjects with liver metastases OR Patients with documented liver or bone metastases: alkaline phosphatase $\leq$ 5 x ULN
Serum Albumin	$\geq$ 2.5 g/dL
Coagulation	
International Normalized Ratio (INR) or Prothrombin Time (PT)	$\leq$ 1.5 x ULN unless subject is receiving anticoagulant therapy as long as PT or PTT is within therapeutic range of intended use of anticoagulants

Activated Partial Thromboplastin Time (aPTT)	≤ 1.5 x ULN unless subject is receiving anticoagulant therapy as long as PT or PTT is within therapeutic range of intended use of anticoagulants
--	--

7. For female patients of childbearing potential and male patients with partners of childbearing potential, agreement (by patient and/or partner) to use a highly effective form(s) of contraception (i.e., one that results in a low failure rate [ $< 1\%$  per year] when used consistently and correctly). Must be on acceptable method for at least 30 days prior to 1st dose of trial product and to continue its use for 5 months after the last dose of atezolizumab.
8. Representative formalin-fixed paraffin-embedded (FFPE) tumor specimens in paraffin blocks (blocks preferred) or at least ten 4 $\mu$ m and one 20 $\mu$ m unstained slides, with an associated pathology report. This specimen will be reviewed by a central reader but results of review will not be required prior to registration and treatment of the subject.
  - a. Tumor tissue has to be of good quality based on total and viable tumor content. Fine-needle aspiration, brushing, cell pellet from pleural effusion, bone metastases, and lavage samples are not acceptable. For core needle biopsy specimens, a result of ten 4 $\mu$ m and one 20 $\mu$ m slides of evaluable quality have to be submitted for evaluation.
  - b. Patients who submitted transurethral resection of bladder tumor (TURBT) specimens are required to submit specimens containing muscle invasive component of the bladder tumor as verified by pathology review. If the TURBT specimens do not contain a muscle invasive component (i.e., T2 or greater), then specimens obtained at the time of cystectomy/nephroureterectomy or metastatic spread (i.e., sample from a metastatic lesion) are required. An archival specimen, if available, must also be submitted.
  - c. Patients who do not have tissue specimens meeting eligibility requirements must undergo a biopsy sample collection during the screening period. Acceptable samples include core needle biopsies for deep tumor tissue (resulting in ten 4 $\mu$ m and one 20 $\mu$ m slides of evaluable quality) or excisional, incisional, punch, or forceps biopsy samples for cutaneous, subcutaneous, or mucosal lesions.
  - d. Patients having additional tissue samples from procedures performed at different times during the course of their urothelial carcinoma are requested (but not required) to also submit these samples for central testing. In situations where multiple specimens are received from different sites or at

different times, the highest score will be used for primary and secondary analyses.

- Inclusion for Cohort 1
9. Untreated with chemotherapy for metastatic disease
  10. Have at least one of the following:
    - a. ECOG (Eastern Cooperative Oncology Group) performance status of 2.
    - b. Glomerular filtration rate calculated as creatinine clearance (Cockcroft-Gault formula) of  $\geq 20$  mL/min and less than 60 mL/min
    - c. Hearing loss or neuropathy of any cause Common Terminology Criteria for Adverse Events (CTCAE) Grade  $\geq 2$ .
- Inclusion for Cohort 2
11. Disease progression during or following treatment with at least one platinum-containing regimen (e.g., GC, MVAC, CarboGem, carboplatin-paclitaxel) for inoperable locally advanced or metastatic urothelial carcinoma or disease recurrence, as defined by:
    - a. Regimen is defined as patients receiving at least one cycle of a platinum-containing regimen with response assessment. Patients who received one cycle of a platinum-containing regimen but discontinued due to toxicity are also eligible.
    - b. Patients who received prior adjuvant/neoadjuvant chemotherapy and progressed within 12 months of treatment with a platinum-containing adjuvant/neoadjuvant regimen are considered as second-line patients.
  12. ECOG (Eastern Cooperative Oncology Group) performance status of  $< 2$
  13. Calculated creatinine clearance (Cockcroft-Gault formula) of  $\geq 20$  mL/min
- Exclusion criteria for ALL subjects
1. Any approved anti-cancer therapy, including chemotherapy, within 3 weeks prior to initiation of trial product; the following exceptions are allowed:
    - a. Palliative radiotherapy for bone metastases or non-target soft tissue lesions completed  $> 7$  days prior to baseline imaging.
    - b. Hormone-replacement therapy or oral contraceptives.
  2. Treatment with any other investigational agent or participation in another clinical trial with therapeutic intent within 28 days prior to Day 1 (first dose of trial product) given that all AEs related to prior treatment have resolved to baseline or Grade 1.
  3. Active central nervous system (CNS) metastases defined as computed tomography (CT) or magnetic resonance imaging (MRI)

evidence of progression and prior radiographic assessments or Leptomeningeal disease.

Subjects that have had prior diagnosis need to have stable disease by having results or performing CT/MRI with 1 month prior to 1st dose of treatment.

4. Uncontrolled tumor-related pain:
  - a. Patients requiring pain medication must be on a stable regimen at trial entry.
  - b. Symptomatic lesions amenable to palliative radiotherapy (e.g., bone metastases or metastases causing nerve impingement) should be treated prior to trial entry.
  - c. Asymptomatic metastatic lesions whose further growth would likely cause functional deficits or intractable pain (e.g., epidural metastasis that is not currently associated with spinal cord compression) could be considered for loco-regional therapy if appropriate prior to first dose of trial product.
5. Uncontrolled pleural effusion, pericardial effusion, or ascites requiring recurrent drainage procedures (once monthly or more frequently)
  - a. Patients with indwelling catheters (e.g., PleurX) are allowed.
6. Uncontrolled hypercalcemia (> 1.5 mmol/L ionized calcium or Ca > 12 mg/dL or corrected serum calcium > ULN) or symptomatic hypercalcemia requiring continued use of bisphosphonate therapy or denosumab:
  - a. Patients who are receiving bisphosphonate therapy or denosumab specifically to prevent skeletal events and who did not have a history of clinically significant hypercalcemia are eligible.
  - b. Patients who are receiving denosumab prior to first dose of trial product have to be willing and eligible to receive a bisphosphonate instead while in the trial.
7. Malignancies other than urothelial carcinoma within 3 years prior to Day 1, with the exception of those with a negligible risk of metastasis or death treated with expected curative outcome (such as adequately treated carcinoma in situ of the cervix, basal or squamous cell skin cancer, or ductal carcinoma in situ treated surgically with curative intent) or localized prostate cancer treated with curative intent and no intent for further treatment or incidental prostate cancer (T1/T2b, Gleason score ≤ 7 undergoing active surveillance and treatment naive).
8. Pregnant and lactating women.

9. History of severe allergic, anaphylactic, or other hypersensitivity reactions to chimeric or humanized antibodies or fusion proteins, or aminoglycoside antibiotics or egg products, poxvirus-based vaccinations, or beef or bovine meat.
10. Known hypersensitivity or allergy to biopharmaceuticals produced in Chinese hamster ovary cells or any component of the atezolizumab formulation.
11. History of autoimmune disease, including but not limited to myasthenia gravis, myositis, autoimmune hepatitis, systemic lupus erythematosus, rheumatoid arthritis, inflammatory bowel disease, vascular thrombosis associated with anti-phospholipid syndrome, granulomatosis with polyangiitis, Sjogren's syndrome, Guillain-Barre syndrome, multiple sclerosis, vasculitis, or glomerulonephritis.
  - a. Patients with a history of autoimmune-related hypothyroidism on a stable, maintenance dose of thyroid replacement hormone with evidence of adequate control or response by TSH (per institution standards) and compliance with prescribed hormone replacement are eligible for this trial.
  - b. Patients with controlled Type I diabetes mellitus on a stable dose of insulin and who are compliant with insulin regimen are eligible for this trial.
  - c. Patients with history of vitiligo and controlled psoriasis are eligible for the trial.
12. History of idiopathic pulmonary fibrosis, organizing pneumonia (e.g., bronchiolitis obliterans), drug-induced pneumonitis, idiopathic pneumonitis, or evidence of active pneumonitis on screening chest CT scan
  - a. History of radiation pneumonitis in the radiation field (fibrosis) is permitted.
13. Positive test for Human Immunodeficiency Virus (HIV).
14. Patients with active hepatitis B virus (HBV; chronic or acute, defined as having a positive hepatitis B surface antigen [HBsAg] test at screening) or hepatitis C virus (HCV)
  - a. Patients with past HBV infection or resolved HBV infection (defined as the presence of hepatitis B core antibody [HBcAb] and absence of HbsAg, negative polymerase chain reaction (PCR) for HBV) are eligible. HBV Deoxyribonucleic Acid (DNA) PCR must be obtained in these patients prior to Day 1.
  - b. Patients positive for HCV antibody are eligible only if polymerase chain reaction is negative for HCV Ribonucleic Acid (RNA) prior to first dose of trial product.

15. Active tuberculosis.
16. Signs or symptoms clinically significant of infection within 2 weeks prior to Day 1.
17. Received therapeutic oral or intravenous (IV) antibiotics within 1 week prior to Day 1
  - a. Patients receiving prophylactic antibiotics (e.g., for prevention of a urinary tract infection or to prevent chronic obstructive pulmonary disease exacerbation) are eligible.
18. Significant cardiovascular disease, which includes but is not limited to New York Heart Association (NYHA) Heart Failure Class II or greater, myocardial infarction within the previous 3 months, unstable arrhythmias, unstable angina.
  - a. Patients with known coronary artery disease, congestive heart failure not meeting the above criteria, or left ventricular ejection fraction < 50% on a stable medical regimen that was optimized in the opinion of the treating physician, in consultation with a cardiologist if appropriate, are eligible.
19. Major surgical procedure other than for diagnosis within 28 days prior to Day 1 or anticipation of need for a major surgical procedure during the course of the trial.
20. Prior allogeneic stem cell or solid organ transplant.
21. Administration of a live, attenuated vaccine within 4 weeks before Day 1 or anticipation that such a live attenuated vaccine would be required during the trial
  - a. Influenza vaccination may be given during influenza season only (approximately October to March). Patients cannot receive live, attenuated influenza vaccine (e.g., FluMist®) within 4 weeks prior to Day 1 or at any time during the trial.
22. Any other diseases, metabolic dysfunction, physical examination finding, or clinical laboratory finding giving reasonable suspicion of a disease or condition that contraindicated the use of an investigational drug or that could affect the interpretation of the results or render the patient at high risk from treatment complications.
23. Prior treatment with CD137 agonists or immune checkpoint blockade therapies, including anti-CTLA-4, anti-PD-1, and anti-PD-L1 therapeutic antibodies
24. Treatment with systemic immunostimulatory agents (including but not limited to IFNs, interleukin [IL]-2) within 6 weeks or five half-lives of the drug, whichever was shorter, prior to Day 1.

25. Treatment with systemic corticosteroids or other systemic immunosuppressive medications (including but not limited to prednisone, dexamethasone, cyclophosphamide, azathioprine, methotrexate, and anti-tumor necrosis factor [anti-TNF] agents) within 2 weeks prior to Day 1, or anticipated requirement for systemic immunosuppressive medications during the trial
- a. Patients who receive acute, low-dose, systemic corticosteroid medications (e.g., a one-time dose of dexamethasone for nausea) or for prevention of hypersensitivity reactions to contrast agents may be enrolled in the trial.
  - b. The use of inhaled, nasal, ophthalmic, intra-articular, auricular or topical corticosteroids, physiologic replacement doses of glucocorticoids (i.e., for adrenal insufficiency), and mineralocorticoids (e.g. fludrocortisone for adrenal insufficiency) is allowed.

Statistical  
considerations

Simon's two-stage design ([Simon, 1989](#)) will be used within each cohort. Due to the multiple testing involved in having two cohorts, the individual cohort alpha has been set to 0.025 (one-sided) to ensure a trial-wide type I error rate of  $\alpha < 0.05$ .

The design for the first cohort, platinum ineligible subjects, is based on a prior published ORR of 23% for atezolizumab monotherapy ([Balar et al., 2017b](#)). The null hypothesis that the true ORR is 0.23 will be tested against a one-sided alternative. In the first stage, 14 subjects will be accrued. If there are 3 or fewer responses in these 14 subjects, the cohort will be stopped. Otherwise, 19 additional subjects will be accrued for a total of 33. The null hypothesis will be rejected if 13 or more responses are observed in 33 subjects. This design yields an actual 1-sided type I error rate of 0.0244 and power of 0.7027 when the true ORR is 0.43 for the combination.

The design for the second cohort, platinum refractory subjects who are anti-PD-L1 naïve, is based on a prior published ORR of 15% for atezolizumab monotherapy ([Rosenberg et al., 2016](#)). The null hypothesis that the true ORR is 0.15 will be tested against a one-sided alternative. In the first stage, 13 subjects will be accrued. If there are 2 or fewer responses in these 13 subjects, the cohort will be stopped. Otherwise, 22 additional subjects will be accrued for a total of 35. The null hypothesis will be rejected if 10 or more responses are observed in 35 subjects. This design yields an actual 1-sided type I error rate of 0.0249 and power of 0.7092 when the true ORR is 0.33 for the combination.

Based on simulations with the two-stage, two-cohort design, the overall type-1 error rate will be approximately 4.7%, and the power for the study, indicating at least one of the two cohorts will be positive given the alternative hypotheses are true, is approximately 91%.

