Women and men of reproductive potential must consent to use of highly effective method of contraception at least 30 days prior to first dose of trial product and continue for 5 months after the last dose of atezolizumab (see Appendix 1, [Section 17.1](#)) and the method(s) used by each subject must be documented. This list does not apply to subjects with same sex partners or for subjects who are and will continue to be abstinent from penile-vaginal intercourse on a long term and persistent basis, when this is their preferred and usual lifestyle.

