### 4.2.5 Premature Discontinuation

#### 4.2.5.1 Discontinuation from Treatment

Subjects may discontinue from treatment at any time. The decision to discontinue trial product may be made by the sponsor, investigator or the subject due to, but not limited to, the following:

- Subject's request to discontinue (withdrawal of consent to participate).
- Subject's unwillingness or inability to comply with trial requirements.
- Occurrence of an AE or SAE attributable to a particular agent may result in discontinuation of that agent. The other agent can be continued until other stopping criteria are met.
- Progressive disease (PD) according to RECIST 1.1 ([Section 17.4](#)). Note: The only exception to this reason for treatment discontinuation is when the investigator feels the RECIST PD may correspond to a pseudoprogression. In this case the investigator is allowed to continue the treatment and schedule a new tumor evaluation as per iRECIST guidance ([Seymour et al., 2017](#)). The clinical conditions suggesting pseudoprogression include symptoms improvement or stabilization, absence of ECOG PS deterioration and absence of unequivocal laboratory parameters or signs of

progression. A 3.6% of ORR have been reported with atezolizumab treatment beyond progression in a post hoc analysis of IMvigor210 Cohort 2 (Necchi et al., 2017).

- Clinical deterioration without radiographic progression.
- Initiation of any other anti-cancer treatment not allowed by the protocol.
- Any reason that, in the opinion of the investigator, precludes the subject from receiving further trial product.
- The trial is stopped or suspended on medical, scientific, or other grounds.

The following procedures must be followed for subjects who discontinue prematurely from trial product:

- If the subject is unable or unwilling to attend all planned visits, every attempt should be made to perform at least a final concluding safety visit, i.e., End of Treatment (EOT) Visit 14/Week 100 within 28 days of withdrawal.
  - If progression is observed on the CT scan scheduled per protocol or decided ahead of protocol-schedule for clinical reasons, CT scan does not have to be repeated.

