### 8.2.8 Pregnancy

Women of childbearing potential (WOCBP) and partners of participating males must be using acceptable method of contraceptive measures as outline in [Appendix 1, Section 17.1](#) for 30 days prior to the first vaccination on Day 1, throughout the entire trial and for 5 months after the last dose of atezolizumab. WOCBP subjects will have a pregnancy test (serum or urine) at every visit including atezolizumab infusion only visits which occurs every 3 weeks.

Any pregnancy (participating females and female partners of participating males) that occurs during trial participation must be reported using a clinical trial pregnancy form. To ensure subject

safety, each pregnancy must be reported to BN or designee within 24 hours of learning of its occurrence and should follow the procedures outlined in [Section 8.3.3](#).

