## 17 Appendices

### 17.1 Appendix 1: Contraception Eligibility Criteria for Female and Male Subjects

A woman is considered of childbearing potential unless post-menopausal (defined as  $\geq 12$  months without a menstrual period) or surgically sterilized. A female subject is eligible to participate if she is not pregnant (as confirmed by a negative  $\beta$ hCG test), not lactating, and at least one of the following conditions applies:

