#### **LESS EFFECTIVE METHODS OF CONTRACEPTION**

Diaphragm with spermicide

Cervical cap with spermicide

Vaginal sponge

Male condoms with spermicide

Male Condom without spermicide

Progestin only pills by WOCBP subject or male subject's WOCBP partner

Female Condom\*\*

\*\* A male and female condom must not be used together

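### Inclusion 7, Section 4.2.1, Section 8.2.8 and Appendix 1 do not state one contraception standard or one duration

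*Protocol*

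**What the plan says.** **Method.** Inclusion 7 (Protocol Section 1.4) asks women of childbearing potential, and men with partners of childbearing potential, for "agreement (by patient and/or partner) to use a highly effective form(s) of contraception", and gives a failure rate below 1% per year as the meaning. Its next sentence calls the same requirement an acceptable method. For subjects of either sex with reproductive potential, Section 4.2.1 says that they "must consent to use of highly effective method of contraception at least 30 days prior to first dose of trial product". It points to Appendix 1. Section 8.2.8 says that women of childbearing potential and partners of male subjects "must be using acceptable method of contraceptive measures as outline in" Appendix 1.

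Appendix 1 (Section 17.1) is titled as eligibility criteria. A female subject may participate if she is not pregnant, "not lactating, and at least one of the following conditions applies". Two lists follow. The first is headed as highly effective. The second is headed "LESS EFFECTIVE METHODS OF CONTRACEPTION" and includes the vaginal sponge, the cervical cap with spermicide and the male condom without spermicide. A note on abstinence says that subjects choosing it need no second method.

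**Duration.** Under inclusion 7 subjects are "to continue its use for 5 months after the last dose of atezolizumab", and Section 4.2.1 gives the same end point. Section 8.2.8 requires contraception "throughout the entire trial and for 5 months after the last dose of atezolizumab". Appendix 1 gives no end point.

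**Dosing.** If an adverse event attributable to one agent leads to that agent being stopped, Section 4.2.5.1 says: "The other agent can be continued until other stopping criteria are met".

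**The concern.** Contraception is both an entry condition and a safety rule here, so a site should find the same answer wherever it looks. A site checking method against Appendix 1 could take one less effective method as sufficient, although inclusion 7 would not accept it. A site or subject looking only at inclusion 7 or Section 4.2.1 would learn of an end date tied to atezolizumab and nothing about CV301, although either agent may continue without the other.

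The protocol itself treats exposure to CV301 in pregnancy as important. Section 8.3.3 stops both products in a pregnant subject, mentions possible transmission through semen, sets a notification window of 30 days after the last CV301 dose beside the 5-month one for atezolizumab, and says that there are no data from which to identify a risk with CV301. None of the contraception passages has an end point counted from the last CV301 dose.

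**Working it through.** The plan states no figure to reproduce. The check sets the texts side by side and then compares dates.

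| Place in protocol | Method standard | End of the requirement |
|---|---|---|
| Inclusion 7 | Highly effective, failure below 1% per year; then called acceptable | 5 months after last atezolizumab |
| Section 4.2.1 | Highly effective; refers to Appendix 1 | 5 months after last atezolizumab |
| Section 8.2.8 | Acceptable, as in Appendix 1 | Entire trial, and 5 months after last atezolizumab |
| Appendix 1 | At least one condition (female subjects); two lists follow | None stated |

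**Step 1, method.** Nothing in Appendix 1 excludes the less effective list or requires two methods to be combined. Read literally, one method from that list meets the appendix and fails inclusion 7. The note exempting abstinent subjects from a second method implies a two-method rule, but none is stated anywhere. The sentence with the at-least-one condition is written for female subjects; the appendix has no matching sentence for men.

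**Step 2, where the end dates part.** Inputs: scheduled CV301 days 1, 22, 43, 64, 85, 106, 148, 190, 274, 358, 442, 526, 610 and 694 (Section 1.5); atezolizumab every 21 days. Assumption: one month is 30.4375 days, the conversion used in SAP Section 4.4.7.5, so 5 months is 5 × 30.4375 = 152.2 days.

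End date under inclusion 7 or Section 4.2.1 read alone = day of last atezolizumab + 152.2.

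- Last atezolizumab Day 106: 106 + 152.2 = 258.2. Six scheduled CV301 days are later (274, 358, 442, 526, 610, 694).
- Last atezolizumab Day 358: 358 + 152.2 = 510.2. Three are later (526, 610, 694).
- Threshold: 694 − 152.2 = 541.8. With a last atezolizumab dose on or before Day 541, the end date in these two places comes before the Day 694 CV301 dose.

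**Step 3, the same dates under Section 8.2.8.** The whole trial is covered, so no scheduled CV301 dose falls outside the required period, whenever atezolizumab stops.

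Step 2 therefore measures how far two wordings disagree. It is not a gap that the protocol allows, and it arises during dosing only for a subject who continues CV301 alone.

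**Step 4, meaning of the entire trial.** Section 4.3 counts up to 2 years of long-term follow-up within a total of up to 4 years per subject. If Section 8.2.8 includes that follow-up, its period also differs from the other two after dosing has ended. The text does not say.

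**The case against.** The strongest reply is that the protocol already answers both halves. Section 5.2 admits a subject only if all inclusion criteria apply, so Appendix 1 cannot relax inclusion 7. The first list carries the same label as the criterion, the second is openly called less effective, and the abstinence note speaks of highly effective alternatives if abstinence is given up. The word acceptable in Section 8.2.8 proves little, because inclusion 7 uses it too. On duration, Section 8.2.8 is mandatory and covers every CV301 dose. Women of childbearing potential are tested for pregnancy at every visit, a pregnant subject receives no more doses, and Section 2.4 says that fowlpox vectors do not replicate in human cells.

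Much of this stands, and it rules out two stronger readings. A reader might infer that contraception may lapse while CV301 is still given; Section 8.2.8 does not permit that. A reader might also infer that a less effective method alone is valid for entry; inclusion 7 still excludes it.

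What the reply leaves open is the wording. Appendix 1 is presented as eligibility criteria and gives its second list no stated role. The place that decides eligibility and the place that says what subjects must consent to both give the shorter period. Pregnancy testing detects a pregnancy rather than preventing it, and does not cover partners.

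**Conclusion.** The point holds as an internal inconsistency of two kinds. First, a highly effective method is required in inclusion 7 and Section 4.2.1, while Appendix 1 lists less effective methods under its at-least-one condition without saying that they do not qualify alone. Second, inclusion 7 and Section 4.2.1 state a different duration from Section 8.2.8, and the difference bears on dosing when CV301 continues after atezolizumab has stopped.

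The size is small. The documents do not say how many subjects would be of childbearing potential or have such partners. Section 2.1 gives a median age at diagnosis of 73 years for bladder cancer, which suggests few, though male subjects with partners also count. Sample size, type I error, power and the endpoint analyses are unaffected. The conclusion rests on the current wording alone. It takes no view on which method standard or interval is right.

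**What to change.** Reconcile inclusion 7, Section 4.2.1, Section 8.2.8 and Appendix 1:

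- State one method standard, using one term for it throughout.
- In Appendix 1, say what part the less effective list plays in eligibility, and either state the rule that the mention of a second method presupposes or remove the mention. Make clear how the at-least-one condition applies to female and male subjects.
- Give the same duration in inclusion 7, Section 4.2.1 and Section 8.2.8, state whether and how CV301 doses count towards it, and say whether the entire trial includes long-term follow-up. Appendix 1 states no duration and needs none for consistency.

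The sponsor decides the standard and the interval. The cost is protocol wording, with matching consent wording where it repeats the rule. The SAP needs no change, since its Section 2.5 refers to the protocol for eligibility.
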